7.10. Demographics and Baseline Characteristics

The baseline demographics and anatomic characteristics of the treatment group will be presented with descriptive statistics.

7.11. Subgroup and Other Analyses

Subgroup analyses will be performed on target lesions of the superficial femoral, popliteal and tibial arteries. The analyses will comprise descriptive analyses of the primary and secondary effectiveness endpoints.

7.12. Changes to Planned Analyses

All analyses will be detailed in the Statistical Analysis Plan (SAP). Any changes to the planned analyses will be documented as amendments to the SAP and in the study report.

7.13. Interim Analyses

The Data Safety Monitoring Board (DSMB) will review safety data (including components of the primary effectiveness endpoint, since these may impact safety) to ensure that it is ethical to continue the study, based on the absence of unacceptable risks to the subject.

There will be a descriptive safety and effectiveness analysis of the primary endpoints after 25 subjects have reached the 30 day follow-up milestone. Enrollment will not stop during this analysis. The results of this analysis will not be made public before the formal primary endpoint analysis and may be used for regulatory submission(s).

7.14. Assessment of Data Poolability

Poolability of data across clinical study sites is justified on a clinical basis (i.e. all study sites use the same protocol) the sponsor monitors the site for protocol compliance, and the data gathering instruments are identical. The Food and Drug Administration also requires a statistical assessment of poolability. This is done by comparing the baseline characteristics across study sites. For categorical baseline variables, such as sex, a generalized Fisher's exact test or equivalent test will be used and for quantitative variables, parametric or non-parametric analysis of variance (general linear models or an equivalent procedure) will be used.

The above statistical analyses do not result in an impediment to pooling, but rather assess the balance of baseline covariates across study sites. If any baseline covariate is found to be statistically significant by this process, multivariate analyses will be done to determine if the imbalance affected study outcome. This is done by using both the variable found out of balance and study site as possible covariates.

It may be necessary to combine two or more low enrolling study sites into pseudo-sites to allow these analyses. Sites with fewer than 6 subjects will be ranked by enrollment from low to high. Starting from the lowest enrollment site, sites will be combined into a pseudo site until the combined size reaches the median enrollment among all sites. This process will be repeated until all resulting sites have enrollment equal to or greater than 6 subjects. This will be done in a manner to preserve the structure of the study and prevent bias.

Baseline characteristics to be considered as possible covariates are as following:

- Age
- Sex
- Coronary artery disease
- Chronic obstructive pulmonary disease
- Myocardial infarction
- Hyperlipidemia
- Cerebrovascular accident
- Hypertension
- Diabetes
- History of tobacco use
- History of peripheral vascular disease
- Rutherford Category
- ABI/TBI

If there are relatively few missing data points (e.g., <10%) for a given variable, a simple sex-specific imputation using the mean (for continuous variables) or median (for dichotomous or categorical variables) of the non-missing values will be done. If there are >10% missing, the variable will be excluded from the imputation analysis.

Poolability analysis will also be performed on the primary endpoints comparing across sites after adjusting for covariates difference. Logistic regression model will be utilized to include unbalanced covariates and site as an independent variable, and the study outcome as dependent variable to assess outcome difference. If the p-value of site effect is less than 0.10, further analyses will be undertaken to investigate the imbalance of the study outcome.

8. ASSESSMENTS AND FOLLOW-UP SCHEDULE

Subjects will undergo the assessments depicted in 6.

8.1. Screening/Baseline Assessment

An initial evaluation will be used to determine if a subject may be considered for enrollment. This evaluation includes an assessment of diagnostic testing that would have been done as part of a subject's routine care. The final disposition (e.g., enrollment, ineligibility, or decision by the subject or physician not to enroll) must be noted. The following must be completed in order to screen a potential subject for participation:

- Review inclusion/exclusion to ensure subject meets criteria.
- Provide a lesion morphology/characterization from lower extremity perspective.

If the subject meets all inclusion and exclusion criteria, and anatomical features for the atherectomy procedure, the subject may be invited to participate in the study. Clinical center personnel will complete a Device Order Form and fax or email it to Rex Medical.

The data captured for the Screening Visit may be gathered over the course of more than one office visit; however, the data must have been obtained within 30 days of the scheduled procedure date. Specifically, the following windows apply to these assessments:

- Duplex Ultrasound or angiography – Within 90 days of index procedure
- Ankle-Brachial Index/Toe-Brachial Index – Within 30 days of index procedure
- Rutherford Classification – Within 30 days of index procedure
- Baseline Labs – Within 30 days of index procedure

The following procedures will be performed at the Screening visit prior to the procedure. All data must be recorded in the subject's case report form (CRF):

- Demographic information
- Physical examination
- Medical history including risk factors
- Patient-reported outcomes questionnaire
- Serum or urine pregnancy test for females of childbearing potential who must have a negative test at baseline and must be using a medically acceptable method of birth control or be postmenopausal or surgically sterile. Acceptable methods of birth control include: barrier method with spermicide, steroidal contraceptive, contraceptives in conjunction with a barrier method, intrauterine device (IUD), or abstinence.

Clinical laboratory tests are expected to be performed at this visit to establish baseline levels (i.e., creatinine, platelet counts and INR if subject is on warfarin). The panel of tests standardly performed at the institution for patients with similar conditions related to PAD should be considered. It is recognized that specific panels may vary between institutions. Laboratory data will not be specially analyzed but will be used only to support adverse event evaluations.

8.2. Point of Enrollment

Subjects will be consented prior to the index procedure, at a point where the anatomic eligibility criteria may be unknown to the Investigator. Enrollment in the study will occur at the point of insertion of the study device into the vasculature, when the device enters the portion of the sheath/guide that resides within the subject's arterial tree.

8.3. Treatment Assessment

Atherectomy using the Revolution™ Peripheral Atherectomy System is considered the treatment phase of the study. The procedure is conducted under fluoroscopic/angiographic guidance. Refer to the Instructions for Use (IFU) for techniques and methods for device deployment.

Anticoagulation therapy to ensure an activated clotting time of 250 – 300 seconds is recommended. Investigator discretion is advised regarding antiplatelet therapy and blood pressure adjustment.

Subjects who require conversion to open surgery due to treatment failure with the device will be followed at each of the follow-up visits specified in **Table 6**.

The following data are to be recorded on the subject's Treatment CRF.

- Procedure time (first cut to last stitch)
- Device runtime, passes and issues
- Description of adjunctive therapy used post-atherectomy
- Blood loss and replacement fluids (blood products) administered
- Vascular access artery
- Proximal device placement location
- Required additional procedures prior, post and/or during atherectomy procedure
- Anticoagulation use during the procedure (agent, total dose)
- AE observation, evaluation, and treatment

Table 6. Schedule of relevant assessments

Assessment	Screening/ Baseline	Treatment	Discharge	1m ± 1 week	6m ± 2 weeks	Unscheduled Visits ^j
Informed consent	Within 30 days of index procedure					
Medical history	Within 30 days of index procedure					
Verify inclusion/exclusion criteria	Within 30 days of index procedure					
Pregnancy testing for female patients of childbearing potential	Within 7 days of index procedure					
Physical examination with peripheral vascular assessment	Within 30 days of index procedure					X
Examination of access site and assessment of healing			X			
Ankle- or toe-brachial index	Within 30 days of index procedure			X	X	X
Rutherford Category	Within 30 days of index procedure			X	X	
Duplex ultrasound examination or angiography	Within 90 days of index procedure			X	X	X
Adverse event assessment		X	X	X	X	X
Patient-reported outcome questionnaires	Within 30 days of index procedure			X	X	

8.4. Hospital Discharge Assessment

Subjects will be evaluated during the time after procedure completion and prior to hospital release. The following information will be collected on the Hospital Discharge CRF:

- Time spent in ICU (hours) and hospital (days)
- Examination of incision site and assessment of healing
- AE observation
- Replacement fluids (blood products) administered post procedure

^j Ankle- or toe-brachial indices and duplex ultrasound/angiography are only required at unscheduled visits if the reason for the unscheduled visit was related to target limb symptoms.

8.5. Follow-Up Assessment

Follow-up evaluation will be scheduled for 30 days (± 1 week) and 6 months (± 2 weeks) post-procedure. The following assessments and procedures will be performed at the 30-day and 6-month follow-up visits:

- Lesion morphology/characterization assessed by duplex ultrasound/angiography
- AE observation

8.6. Secondary Interventions

Subsequent to treatment, conditions warranting additional treatment (e.g., restenosis) may present. Any intervention taken to treat a condition involving the initially-treated lesion shall be documented on the Additional Treatment CRF. Additional Revolution™ devices may be provided for conditions involving the initially-treated lesion. Since such procedures would be secondary interventions, repeating the determination of eligibility and consenting are not required unless mandated by institutional policies.

Additional Revolution™ devices may not be used for other lesions or conditions without prior written approval from the Sponsor. Such procedures must be presented in advance to the US Food and Drug Administration (FDA) and Institutional Review Board (IRB) unless deemed emergent. In either case, the use of the Revolution™ device for other lesions/conditions shall be treated as a protocol deviation.

8.7. Unscheduled Post Treatment Follow-up Visits

If a subject returns to the institution between scheduled follow-up visits for matters related to the study procedure, the visit will be treated as an unscheduled visit and the assessments completed at this visit will be done at the discretion of the Investigator. CRF pages are provided for unscheduled visits and contain the same information as all the follow-up visits, in addition to the reason for the visit.

8.8. Withdrawals and Loss to Follow-up

Participation is completely voluntary and each subject is free to withdraw from the study at any time. An investigator also has the right to withdraw the subject from the study in the event of reasons concerning the health or well-being of the subject, or in the case of lack of cooperation. Should a subject decide to withdraw for any reason, or should the investigator decide to withdraw the subject, all efforts will be made to complete and report the observations up to the time of withdrawal as thoroughly as possible. A complete final evaluation at the time of the subject's withdrawal must be made and an explanation given of why the subject is withdrawing or being withdrawn from the study.

The reason for and date of withdrawal must be recorded on the subject's End of Study CRF. If the reason for the withdrawal is a device-related or procedure related AE, the event must be reported to the Sponsor and recorded in the CRF.

If the procedure is aborted, the subject does not need to complete the follow-up assessments, unless the subject is converted to surgical repair. The subject's enrollment roster position may not be made available to other subjects.

If a subject dies during the course of the study, the Sponsor will request an autopsy provided the subject authorized an autopsy in the event of death during the course of the study. Autopsy observations should include documentation of condition of body organs and determination of device and/or procedure relationship to death.

All efforts will be made to retain subjects in order to collect data at all the follow-up visits (30 days, 6 months). Due diligence in reaching the subject must be made by:

- Two documented telephone contact attempts, emails, or regular postal mail letters; and
- Certified letter

After the above attempts were made, if no response is obtained, the final evaluation of a given subject will be the last visit at which study-related procedures were performed on that subject. The End of Study CRF page will need to be completed and communication attempts will need to be documented.

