3.1 Intention-To-Treat (ITT) Analysis

The ITT analysis will be performed on all enrolled subjects in whom the study device entered the vasculature, irrespective of adherence with the entry criteria, treatment actually received, subsequent withdrawal, or deviation from the investigational plan. Analysis of safety outcomes will use the ITT population.

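### The plan has no active MAE or vital-status follow-up after investigator withdrawal, and the SAP drops event-free leavers before day 23 from a safety set defined as ITT

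*Protocol*

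**What the plan says.** **Withdrawal.** Under Protocol 8.8 an investigator may "withdraw the subject from the study in the event of reasons concerning the health or well-being of the subject, or in the case of lack"; the sentence ends by naming cooperation as what is lacking. For any withdrawn subject, "all efforts will be made to complete and report the observations up to the time of withdrawal as thoroughly as possible". There is one further requirement: "A complete final evaluation at the time of the subject's withdrawal must be made". The reason and date go on the End of Study CRF, and a device- or procedure-related adverse event that causes withdrawal must be reported.

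**Aborted procedures.** The same section says: "If the procedure is aborted, the subject does not need to complete the follow-up assessments", with an exception for conversion to surgical repair. Under Protocol 6.5 and 8.2 a subject is enrolled once the device enters the vasculature, so such a subject can already belong to the ITT set.

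**Event reporting.** Protocol 10.1 and 10.2 make deaths and device- or procedure-related adverse events reportable. Neither section says whether this continues after withdrawal.

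**Safety population.** SAP 3.1 states: "Analysis of safety outcomes will use the ITT population". That population is analysed "irrespective of adherence with the entry criteria, treatment actually received, subsequent withdrawal, or deviation from the investigational plan"; Protocol 6.5 has the same definition.

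**Safety denominator.** SAP 4.7 and 5.1 restrict the 30-day rate to evaluable subjects: those with an event by day 30, those with follow-up at or after day 23, and those whose consent-withdrawal or recorded loss date is at or after day 23. The imputation and tipping-point analysis in Protocol 7.6 and SAP 4.7 are described for missing effectiveness data only.

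**The concern.** Health or well-being is a reason tied to prognosis, and the treating investigator applies it in a single-arm trial against a fixed goal. Suppose a subject with a worsening limb is withdrawn on day 12 and has a major amputation on day 20. Section 8.8 sets no active follow-up that would find the amputation. If it stays unknown, SAP 5.1 treats the subject as not evaluable, and the subject leaves both numerator and denominator.

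A subject who leaves event-free on day 25 stays in the denominator as MAE-free, although days 26 to 30 were not observed.

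Both routes can make the observed MAE-free proportion higher than the true one. The Clinical Events Committee can adjudicate only events that reach it, and no sensitivity analysis for missing safety data is specified. At stake is the validity of one of the two endpoints that decide study success. Technical success is measured at the index procedure, so later withdrawal does not affect it.

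**Working it through.** **Inputs from the documents** (Protocol 7.2, 7.4, 7.9; SAP 3.3, 4.4, 5.1): performance goal 80% MAE-free; expected 91%; exact binomial test, one-sided 0.025; 110 evaluable and 121 enrolled after 10% attrition; lower window limit day 23.

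**Assumed, because the documents give neither:** the number w of event-free leavers before day 23, and their own 30-day MAE risk q.

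**1. The plan's sample size.** The normal approximation gives n = [(1.96·√(0.80·0.20) + 1.2816·√(0.91·0.09)) / 0.11]² = [(0.784 + 0.367) / 0.11]² ≈ 109.4, so 110. Enrolment is 110 × 1.10 = 121. Exact power at 110 is 88.2%; the first n with at least 90% is 107 (90.02%). The stated figure is reproduced closely enough and is not the issue.

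**2. Pass rule.** Find the smallest r with P(X ≥ r) ≤ 0.025 for X ~ Bin(n, 0.80).

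| n | MAE-free needed | MAEs allowed | Lower limit at the rule | Lower limit with one more MAE |
|---|---|---|---|---|
| 121 | 106 | 15 | 80.4% | 79.4% |
| 118 | 104 | 14 | 80.9% | 79.9% |
| 110 | 97 | 13 | 80.6% | 79.6% |

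**3. Chance of a false pass.** Set the true MAE rate over all 121 at the null, 20%, which is 121 × 0.20 = 24.2 expected events. The rate among those left in the denominator is m = (24.2 − w·q) / (121 − w). The chance of passing is P(X ≥ r) for X ~ Bin(121 − w, 1 − m).

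For w = 11 and q = 40%: m = (24.2 − 4.4) / 110 = 18.0%, and P(X ≥ 97) = 5.4%.

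| Early leavers | q = 20% | q = 40% | q = 60% |
|---|---|---|---|
| 3 | 1.4% | 2.0% | 2.7% |
| 6 | 1.9% | 3.6% | 6.4% |
| 11 | 1.7% | 5.4% | 14.2% |

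When leavers carry average risk (q = 20%) the error stays below 2.5%. With 3 leavers it stays close to nominal even at 60%. With 11 leavers at twice the average risk it is about double the nominal level. Leavers on days 23 to 29 are not in this table; any unseen event among them would push the same way.

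**4. Reversal of a result.** With 11 early leavers, 13 MAEs in 110 pass. Three unseen MAEs among the leavers make 13 + 3 = 16 of 121, which fails. That is the boundary case. At the planned 9% rate about 10 MAEs are expected in 110 (0.09 × 110 = 9.9), and six of the 11 leavers would need an unseen MAE.

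**The case against.** Three stronger readings are tempting, and the documents do not support them.

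- **That withdrawal after a one-time procedure ends nothing except data collection.** Protocol 2.7 continues aspirin through 6 months, Table 6 schedules imaging at 1 and 6 months, and section 8.6 allows further study devices for the treated lesion. Withdrawal for well-being is therefore not an empty act, and this point does not question the investigator's right to it.
- **That nothing requires a later event to be collected.** Protocol 10.1 and 10.2 require deaths and related adverse events to be reported and make no exception for withdrawn subjects. The first criterion in SAP 5.1 counts any event known by day 30, whatever the withdrawal status. A known day-20 death would count. That data stop at withdrawal is an inference from section 8.8 and from the absence of any later provision; it is not stated.
- **That the clause puts the whole 10% allowance at risk.** The allowance covers attrition of every kind, and investigator withdrawals may be a small part of it. Results away from the boundary are much harder to reverse.

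Two further points are fair. The final evaluation and the recorded reason mean that a deteriorating subject does not leave undocumented. The consent pages and the CRF are not available here, so they may already separate stopping visits from withdrawing data consent; only the lack of that distinction in section 8.8 is established.

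What remains is that none of these safeguards actively seeks an event after withdrawal, and the SAP denominator rule still disagrees with the ITT definition.

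**Conclusion.** The concern holds as a gap between documents. Section 8.8 leaves MAE status after withdrawal unsought, SAP 4.7 and 5.1 turn the resulting unknowns into exclusions or successes, and the ITT definition says withdrawal should not matter. Following the plan as written can therefore bias the primary safety test towards a pass.

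The size is conditional. Against a nominal 2.5%, the chance of a false pass is 1.4% to 2.7% with 3 early leavers and 1.7% to 14.2% with 11, for leaver risks of 20% to 60%. These figures assume a true MAE rate of exactly 20% over all 121 and that every leaver's event goes unseen. They are a range, not a forecast. With few leavers, or leavers at average risk, the test keeps its level or nearly so. The point merits correction because ascertainment is cheap and events never collected cannot be recovered later. It does not show that the safety conclusion would be wrong.

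**What to change.** **Protocol 8.8 and the End of Study CRF.** Record stopping study visits separately from withdrawing consent to data collection. State that, unless the subject withdraws that consent, MAE components and vital status are obtained through day 30 and month 6, by telephone or from records, for every enrolled subject. This includes subjects withdrawn by the investigator and those whose procedure was aborted. State in section 10 that event reporting continues on the same terms.

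**SAP 4.7 and 5.1.** Reconcile the adjusted denominator with the ITT definition in SAP 3.1, including the handling of event-free leavers on days 23 to 29. Say how an investigator-decided withdrawal is dated, since the third evaluability criterion names only consent withdrawal and recorded loss. Add a worst-case and a tipping-point analysis of the primary safety endpoint over all enrolled subjects.

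**Cost.** Protocol and CRF wording, possibly a line in the consent form, and record checks on a few subjects. The sensitivity result may be less favourable. At a true 91% MAE-free rate, counting every early leaver as an event gives a 73.7% chance of passing with 3 leavers and 2.6% with 11, against 89.1% and 88.2% when they are dropped. The worst case is therefore a bound to report beside the primary result, and a reason to obtain day-30 status rather than impute it. With status known for all 121, power is 92.3%.

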5. OUTCOME VARIABLES

5.1. Primary Safety Endpoint Definition

The primary safety endpoint is a composite endpoint triggered by the occurrence of any of five categories of events through 30 days after the index procedure.^b These events are the following:

1. All-cause mortality- Death from any cause, from the point of enrollment through 30 days.
2. Clinically-driven TLR- Any revascularization of the target lesion that occurs after the subject has left the procedure room following the index procedure. TLR do not include adjunctive interventions performed during the index procedure, whether planned or for failed atherectomy or for complications of atherectomy. TLR are considered to be clinically-driven when they occur as a

^b The index procedure is considered to occur on day 0; the first post-procedure day is day 1, and so on. The 30-day time point includes any events with a start date prior to 11:59PM on day 30.

result of restenosis >50% diameter reduction as measured angiographically or by duplex ultrasound (occlusion or stenosis with Peak Systolic Velocity Ratio >2.4).^c

3. Perforation of the target vessel- Imaging evidence (standard contrast angiography, computed tomography angiography or open surgical/pathology visualization) of target vessel perforation from any cause. For angiography and CTA, perforation is defined by contrast extravasation outside of the adventitia.
4. Clinically-significant distal embolization- Target limb embolization documented on core laboratory-assessed angiography or with open surgery/pathology, accompanied by symptoms referable to the involved vascular bed.
5. Major amputation- Amputation of the target limb that results in limb shortening; i.e. is performed at or above the level of the malleoli.

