6.5. Study Populations

The point of enrollment in this study occurs when a study device first enters a subject's vasculature.^e The following populations will be analyzed in the study:

Intention to treat (ITT) analysis: The ITT analysis will be performed on all enrolled subjects in whom the study device entered the vasculature, irrespective of adherence with the entry criteria, treatment actually received, subsequent withdrawal, or deviation from the investigational plan.²⁴

Per Protocol analysis: The PP analysis will be performed on target lesions with core laboratory-determined RVD falling within the pre-specified anatomic eligibility criteria of ≤ 4.0 mm. The effectiveness endpoints will be determined using the PP analytic subset to exclude lesions where the largest bore (2.0 mm) study device is less than 50% of the RVD (see Section 7.3, page 22, below).^f

^e This point is defined as entry of the study device into the access sheath/guide at the level where the sheath/guide enters the subject's body.

^f Use of the 2.0 mm bore in a vessel larger than 4.0 mm in diameter would not result in a lumen channel that exceeds 50% of the RVD. In other words, the residual stenosis after successful atherectomy would still not meet the criteria

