5. ENDPOINT ALGORITHMS

5.1 Safety Endpoints

For missing values, an adjustment to the denominator will be made based on the amount of evaluable data for safety-endpoints.

Safety denominator adjustment: For each visit (or reporting time point), the event rate will be calculated as the number of subjects with certain event term over the number of evaluable subjects. The evaluable subjects at each reporting time point include all subjects who are enrolled by the snapshot date and

- 1) Had an event within (on or before) the reporting cutoff days, or
- 2) Had a follow-up at or after the lower limit of the reporting window, or
- 3) The withdrawal consent date/recorded lost-to-follow-up date at or after the lower limit of the reporting window

‘Days to event’ (date of earliest event – date of index procedure) and ‘Days to last contact’ (date of last contact – date of index procedure) are usually used for the determination of the eligibility of the ‘evaluable subject’. The last contact date will be calculated based on the information gathered from all available dates during the follow-ups.

The ‘Reporting Cutoff Days’, ‘Lower limit of the Reporting Window’ and the correspondent visits are as the following:

Visit	Reporting Cutoff Days	Lower Limit of the Reporting Window (days post-index procedure)
1-month	30 days post-index procedure	Days to last contact: 23
6-month	180 days post-index procedure	Days to last contact: 166

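### Subjects aborted after device entry and not converted to surgery are in the safety population but excused from follow-up, so some leave the 30-day MAE denominator for a reason tied to procedural outcome

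*Protocol*

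**What the plan says.** - **Enrolment.** Protocol 6.5: "The point of enrollment in this study occurs when a study device first enters a subject's vasculature". Protocol 8.2 repeats this. Enrolment therefore precedes any atherectomy.
- **Safety population.** The ITT set is all enrolled subjects, "irrespective of adherence with the entry criteria, treatment actually received, subsequent withdrawal, or deviation from the investigational plan" (Protocol 6.5). SAP 3.1 adds: "Analysis of safety outcomes will use the ITT population".
- **Exemption.** Protocol 8.8: "If the procedure is aborted, the subject does not need to complete the follow-up assessments, unless the subject is converted to surgical repair". The next sentence keeps the subject within the planned 121: "The subject's enrollment roster position may not be made available to other subjects". The same section asks for every effort to retain subjects and collect data at the 30-day and 6-month visits.
- **Who is still followed.** Protocol 8.3: "Subjects who require conversion to open surgery due to treatment failure with the device will be followed at each of the follow-up visits".
- **Missing safety data.** SAP 4.7 adjusts the denominator. SAP 5.1 counts a subject as evaluable at 30 days by one of three routes: an event on or before day 30; a later contact ("Had a follow-up at or after the lower limit of the reporting window, or"), with the lower limit at day 23; or a withdrawal or loss-to-follow-up date at or after day 23. The imputation and tipping-point analysis in SAP 4.7 are described only for the effectiveness measurement.
- **Undefined term.** Neither document says what makes a procedure aborted.

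**The concern.** Take a subject in whom the device is inserted, cannot be advanced and is withdrawn, who is not converted to surgery and who goes home without a recorded MAE. SAP 3.1 places this subject in the primary safety analysis. Protocol 8.8 releases the site from the 1-month visit. Without that visit or any other contact from day 23, the subject meets none of the three evaluability routes and leaves the denominator.

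The data are then missing because of how the procedure went, and because the protocol permits it. Recorded MAEs in aborted subjects stay in the numerator, while aborted subjects not known to have an MAE drop out. Death, major amputation and symptomatic embolization after discharge are seen only if the site happens to hear of them. Safety is one of two endpoints that must both succeed (Protocol 7.4, SAP 4.5). The 6-month safety components have the same gap.

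**Working it through.** **Inputs from the documents** (Protocol 7.9, SAP 3.3): goal 80% free of MAE; anticipated 91%; one-sided exact binomial test at 0.025; 110 evaluable and 121 enrolled with 10% attrition.

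**1. The plan's own figure.** Normal approximation: n = [(1.960·√(0.80·0.20) + 1.282·√(0.91·0.09)) / 0.11]² = 109.4, so 110, and 110 × 1.10 = 121. Both match. The exact test at n = 110 needs at least 97 free of MAE and has size 0.0170 and power 88.2%.

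**2. Pass limits** (exact one-sided 97.5% lower confidence limit, LCL, above 80%). With all 121 observed, at most 15 MAEs (106/121 free, size 0.0197). With 115 observed, at most 14 (101/115 free).

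**3. What unseen events could do.** The documents give no abort rate and no MAE rate for aborted subjects. Assume a = 6 of 121 are aborted with status unobserved.

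| Observed | LCL | Unseen MAEs among the 6 | All 121 | LCL |
|---|---|---|---|---|
| 14/115 (12.2%) | 80.4%, met | 2 | 16/121 (13.2%) | 79.4%, missed |
| 10/115 (8.7%) | 84.6%, met | 4 | 14/121 (11.6%) | 81.3%, met |

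From 10/115, reaching the failing count of 16 would take 16 − 10 = 6 unseen MAEs, that is, all six subjects.

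**4. Chance of false success.** Set true freedom from MAE across all 121 at exactly 80%, so that 0.20 × 121 = 24.2 MAEs are expected. If the a unobserved subjects have MAE rate q, freedom among the observed is p = 1 − (24.2 − a·q)/(121 − a). The chance of success is the binomial probability of reaching the pass limit at that p. For a = 6 and q = 50%: p = 1 − 21.2/115 = 0.8157, and P(at least 101 of 115 free) = 0.048.

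| Unobserved a | q = 20% | q = 30% | q = 50% | q = 100% |
|---|---|---|---|---|
| 2 | 0.024 | 0.027 | 0.033 | 0.053 |
| 6 | 0.019 | 0.027 | 0.048 | 0.173 |
| 12 | 0.019 | 0.036 | 0.111 | 0.666 |

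At q = 20% the unobserved subjects are like the rest, and each figure is just the size of the exact test at that n. Below 20% the error runs the other way: for a = 6 and q = 10%, p = 1 − 23.6/115 = 0.7948 and the chance falls to 0.014.

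**5. Power.** Losing 12 subjects to ordinary attrition leaves 109 and 88.8% power. Losing 6 aborted subjects as well leaves 103 and 86.6%. The power loss is modest; the question is bias.

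**The case against.** A reader might infer that 30-day safety goes unobserved in the subjects in whom the device failed, and that this favours the device. The documents do not support that reading.

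- **Failure is not the same as an aborted procedure.** Failures converted to open surgery are followed at every visit. Protocol 5.1 foresees adjunctive treatment for failed atherectomy during the index procedure, and nothing calls that aborted.
- **Waiving visits does not waive reporting.** Adverse events are assessed at treatment and discharge (Protocol Table 6 and 8.4), when procedural perforation or embolization would most likely be seen. Later serious events, deaths and primary-safety events known to the site must be reported (Protocol 10.1 and 10.2), with no exception for aborted procedures. A recorded MAE keeps the subject evaluable.
- **The direction is not established.** Keeping known MAEs and dropping the remaining unobserved subjects is conservative if the unseen MAE rate is low. Nothing in the documents ranks aborted subjects as higher risk.
- **Later revascularization may not count.** Protocol 5.1 covers "Any revascularization of the target lesion that occurs after the subject has left the procedure room following the index procedure", but calls it clinically driven only when it results from restenosis. Whether an untreated lesion can restenose is not stated.
- **The reversal is an edge case.** It needs a result at the pass limit; exactly 14/115 has probability 5.9% at a 9% MAE rate. With 9% in the 115 and six unobserved, the chance that observed success hides failure in all 121 is 0.7%, 3.1% or 7.6% at unobserved rates of 9%, 20% or 33%. At 9% the opposite error is likelier, at 2.2%.

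All of this stands, and it limits the scope and size of the point. It does not close the gap: reporting that depends on the site learning of an event is weaker than asking the subject, and the SAP has no safety analysis that would show the effect.

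**Conclusion.** The point holds for subjects who are aborted after device entry and not converted to surgery. Protocol 8.8 excuses from follow-up people whom SAP 3.1 says are analysed, and SAP 5.1 removes those with no recorded MAE and no contact from day 23. What is lost is active ascertainment of MAE from discharge to day 30, and to 6 months.

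The bias may run in either direction. With six unobserved, the false-success probability moves from 0.019 to 0.048 as their MAE rate goes from 20% to 50%; it exceeds 0.025 only when that rate is well above the 20% null rate. At a result near the planned 9%, even four unseen MAEs leave the goal met. These figures rest on assumed abort counts and event rates. The conflict between the sections does not: it is in the text, affects a primary endpoint, and has to be settled before follow-up is missed, because an analysis can bound uncollected outcomes but cannot restore them.

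**What to change.** 1. **Protocol 8.8:** reconcile it with SAP 3.1 and 5.1 by removing the exemption for adverse event and MAE ascertainment. Every enrolled subject, including those aborted, has 30-day and 6-month MAE status obtained; a visit or telephone contact suffices. Target-lesion imaging may stay exempt where no atherectomy was delivered.
2. **Both documents:** define an aborted procedure, and say whether failed atherectomy completed with adjunctive treatment is one.
3. **SAP 4.7:** add a safety sensitivity analysis on all enrolled subjects. It should count those without 30-day status as MAEs and report the number of such MAEs at which the conclusion changes. The tipping point matters because the worst case alone is severe: with six unknown it allows only 15 − 6 = 9 recorded MAEs in 115, against 0.09 × 115 = 10.35 expected. It should be labelled supportive, not a new success criterion.

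Cost: a few extra contacts, no extra subjects or procedures, and possibly a slightly less favourable MAE rate.
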